# 1.0 Background

Post-inflammatory hyperpigmentation (PIH) is a common occurrence following skin inflammation, whether due to trauma or inflammatory dermatoses, often leading to long-term dyschromia which may last years after the inciting lesion has resolved. PIH is an acquired hyperpigmentation caused by hypermelanosis after cutaneous trauma or inflammation, and while it may occur in any skin type, is more commonly found in darker skin (Fitzpatrick skin types IV-VI). These discolorations often occur on cosmetically sensitive areas, such as the face, and may lead to tremendous psychological impact. Tranexamic acid (TA) is a plasmin inhibitor capable of inhibiting melanogenesis, and has been previously taken orally, injected intradermally, and more recently applied topically for treatment of melasma.

# 2.0 Rationale and Specific Aim

The goal of this study is to determine if topical 5% TA is capable of reducing the severity of PIH following acne vulgaris. Topical hydroquinone represents the current standard of care for PIH, however, common side effects include irritation, erythema, and dermatitis—side effects not reported in topical TA.

## 3.0 Previous Studies

Several studies have demonstrated topical TA provides statistically significant improvements in women with melasma, another cause of hyperpigmentation. Additionally, it has been demonstrated to be equally effective as hydroquinone in reducing melasma hyperpigmentation, however with less adverse effects.

# 4.0 Inclusion/Exclusion Criteria

Inclusion Criteria:

- Age 18-65
- Patients with bilateral involvement of facial PIH secondary to acne vulgaris.

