## **Exclusion Criteria**

- Pregnant patients or patients planning to become pregnant during the time of the study.
- Patients with a history of use of hydroquinone, kojic acid, tretinoin, adapalene, tazarotene or azaleic acid in the previous 3 months
- 5.0 Enrollment/Randomization

Patients presenting to the dermatology clinic with PIH secondary to acne vulgaris and are interested in a potential treatment will be considered as candidates for participation. If their treating physician in clinic determines they are eligible, they will be referred to the PI or sub-PI for screening and consent. The study design and consent will be explained, their expectations for participation will be discussed, and any questions will be addressed. The patient will then have the choice to participate or decline participation in the study. Block randomization will be utilized to determine which side will be the treatment side.

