#### 6.0 Study Procedures

Patients with bilateral disease will be chosen to participate in the study. Patients will be advised to discontinue any other facial cleansers or products prior to beginning treatment. One side of the patient will be chosen as the treatment side, and the other as an intrinsic control. Each day, the participant will wash their face in the morning with a standard cleanser, dry their face, then apply the medication to the treatment side of their face only to areas of unwanted dark spots. The patient will then apply the vehicle to the other side of their face only to the areas of unwanted dark spots. The patient will wait 30 minutes, and then apply a standardized sunscreen SPF 30+ to entire face. Each night, the patient will again wash their face. Patients will participate in a follow-up clinic visit 4 weeks, 8 weeks and 12 weeks after beginning treatment. At each visit, photographs will be taken of their face to monitor progression and to serve as a comparison to the control side. The postacne hyperpigmentation index, a validated system for evaluating hyperpigmentation due to acne vulgaris, will be used to monitor the progression of facial lesions. At week 0 and 12, the patients will take a survey to determine the impact that their facial spots have on their quality of life.

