## 9.0 Statistical Considerations

We will attempt to demonstrate clinical improvement of the postinflammatory hyperpigmentation by decreasing the size, intensity, and number of the facial lesions by comparing the treatment side to the control side of the face.

Patients will be evaluated prior to treatment, and at each follow-up visit both 4 weeks, 8 weeks and 12 weeks post-treatment using the Postacne Hyperpigmentation Index (PAHPI). The scoring system is as follows:

Weighted score (S)		Median lesion size
2		<3 mm
4		3-6 mm
6		7-10 mm
8		>10 mm
Weighted score (I)		Median lesion intensity
3	Slightly darker than surrounding skin	
6	Moderately darker than surrounding skin	
9	Significantly darker than surrounding skin	
Weighted score (N)		No. of lesions
1		1-15
2		16-30
3		31-45
4		46-60
5		>60

 Table I. Scoring the postacne hyperpigmentation index

Total postacne hyperpigmentation index = S + I + N; score range: 6-22.

Using power analysis to determine sample size:

In the study by Kim et al, they demonstrated a significant decrease in melasma, another disorder of facial hyperpigmentation, using topical tranexamic acid. They demonstrated a significant decrease in the melasma area and severity index of approximately 33% with a sample size of 23 patients. For our study, a sample size of 25 patients is sufficient to detect a clinically important difference of 30% between treatment and control sides of the face using a two-tailed z-test of proportions between two groups of 80% power and a p-value of 0.05.

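### Eligibility sets no minimum PAHPI, so sides scoring 6 to 8 on a scale that starts at 6 can enter with little or no room to show improvement

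*Combined protocol and SAP*

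**What the plan says.** Section 4.0 has two inclusion criteria: age 18 to 65, and "Patients with bilateral involvement of facial PIH secondary to acne vulgaris". Neither the exclusion criteria nor sections 5.0 and 6.0 add a minimum score, lesion count, size or intensity. Section 5.0 leaves the judgement to the clinic ("If their treating physician in clinic determines they are eligible") without a severity threshold.

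Section 6.0 sets up a within-patient comparison: "One side of the patient will be chosen as the treatment side, and the other as an intrinsic control". Section 9.0 scores lesions before treatment and at weeks 4, 8 and 12: "Total postacne hyperpigmentation index = S + I + N; score range: 6-22". Table I gives size 2, 4, 6 or 8, intensity 3, 6 or 9, and number 1 to 5.

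The planning target is a "clinically important difference of 30% between treatment and control sides of the face". It follows a melasma result described as a "significant decrease in the melasma area and severity index of approximately 33% with a sample size of 23 patients", but the sizing uses a "two-tailed z-test of proportions between two groups of 80% power and a p-value of 0.05". The text does not say whether the 30% is a fall in score or a gap between proportions of responders.

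**The concern.** A patient with few, small and faint marks on both sides meets every criterion and starts at or just above the bottom of the scale. That patient's treated side can show little or no improvement on the only lesion score in the plan, whatever the product does. With 25 patients, each one is 4% of the sample. Those without room to improve move the mean difference between sides towards zero, so a product that works could look weaker than it is.

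**Working it through.** **The plan's own figure.** Section 9.0 states 25 patients but gives no pair of proportions, responder definition, SD or baseline PAHPI, so 25 cannot be uniquely reproduced. For the named test, with p̄ the mean of p1 and p2, the number per group is

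n = [1.960·√(2p̄(1−p̄)) + 0.842·√(p1(1−p1) + p2(1−p2))]² / 0.30².

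This gives 22 at 0% v 30%, 25 at 3% v 33%, 27 at 5% v 35%, 32 at 10% v 40% and 43 at 35% v 65%. The check below therefore takes 80% power at n = 25 as given and asks what low entry scores would do to it.

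**Which sides can enter low.** Table I has 4 × 3 × 5 = 60 combinations of (S, I, N). Four total 8 or less. The largest fall from score s is (s − 6)/s, and a 30% fall ends at 0.7s.

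| Entry score | Combinations | Largest fall | A 30% fall would end at |
|---|---|---|---|
| 6 | (2,3,1) | 0% | 4.2 |
| 7 | (2,3,2) | 14.3% | 4.9 |
| 8 | (2,3,3), (4,3,1) | 25.0% | 5.6 |
| 9 | (2,3,4), (2,6,1), (4,3,2) | 33.3% | 6.3 |
| 10 | four combinations | 40.0% | 7.0 |

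The lowest score from which a 30% fall stays on the scale is 6/0.7 = 8.57, so 9. Even there 30% is 2.7 of the 3 available points. In general the share of the available range used is 0.3s/(s − 6): 90% at 9, 75% at 10, 56% at 13 and 41% at 22.

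**Between sides.** While the vehicle side stays at 8 or less, the largest gap is (8 − 6)/8 = 25%. If the vehicle side worsens to 9 and the treated side is at 6, the gap is (9 − 6)/9 = 33%.

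**Effect on power (illustration).** A share f of patients is assumed to enter low; the documents do not give f. The analysis is a two-sided 5% paired t-test on 25 differences, with a planned difference of 0.584 SD, which gives 80% power at f = 0. Two cases are simulated for patients at 6: a difference of exactly zero, or a mean of zero with the same SD as everyone else. For patients at 8 who reach their 25% maximum, the retained effect is e = [0.30(1 − f) + 0.25f]/0.30, and power is Φ(2.802e − 1.960) by normal approximation, where 2.802 = 1.960 + 0.842. At f = 10%, e = 0.295/0.30 = 0.983 and power is Φ(0.795) = 79%.

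| Share f | At 6, zero variance | At 6, equal SD | At 8, maximum fall |
|---|---|---|---|
| 10% | 75% | 70% | 79% |
| 20% | 69% | 59% | 77% |
| 30% | 62% | 47–48% | 76% |

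**If 30% is a gap in proportions.** Take 0% v 30% responders among patients who can respond, and let a share f be unable to. The treated proportion becomes 0.30(1 − f), that is 27%, 24% or 21%. Power with 25 per group goes from 87% to 82%, 76% or 69%. The direction is the same.

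**The case against.** A reader might infer that the planned effect is arithmetically impossible for anyone entering at 6 to 8. The documents do not support that without a condition. It needs the 30% to be a percentage fall in PAHPI. The melasma figure suggests this, but the named test compares proportions. On that reading, a patient at 7 or 8 could respond if any improvement counted; only a patient at 6 could not. The 30% is also a difference between sides, and a worsening vehicle side could produce it from a low start, though that would not show the reduction in severity that section 2.0 sets as the goal. Nor does a planned mean have to be reachable in every patient.

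A reader might also apply the larger power losses to all entries at 6 to 8. They belong only to patients with no room at all, and only one of the 60 combinations totals 6. At 8 the loss is 1 to 4 points. How many such patients would come forward is unknown, and people seeking treatment at a dermatology clinic may rarely have marks this faint and small.

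Broad eligibility is a legitimate choice, since section 2.0 does not restrict the question to more severe disease. And a cut-off of 9 is not self-evident: it follows only from a 30% fall and still requires a drop to the floor.

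All of this limits the size of the problem and shapes the remedy. What stands is that no entry minimum exists and that a side at 6 cannot improve on the score under any reading of the 30%.

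**Conclusion.** The point holds in a conditional form. Followed as written, the plan can enrol patients whose treated side cannot improve on PAHPI (score 6) or can improve by at most 14.3% or 25% (scores 7 and 8). A 30% fall in score is out of reach for all of them. Under a responder analysis, those at 6 cannot respond, and those at 7 or 8 could do so only under a lenient definition. The bias is towards no difference. Its size ranges from 1 to 4 points of power (patients at 8) to roughly 5 to 33 points (patients at 6) for shares of 10% to 30%.

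This rests on four assumptions: the shares themselves; 80% power at n = 25 when every patient can show the planned effect; PAHPI scored separately on each side, which the side-to-side comparison requires; and the printed minimum of 6 as the lowest value, since Table I has no score for a cleared side. It is a worthwhile, cheap improvement. It is not evidence that the trial must fail.

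**What to change.** In section 4.0, add an inclusion criterion: a minimum total PAHPI on each side of the face at the pre-treatment evaluation. It should apply to both sides because randomisation decides which one is treated.

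In section 9.0, state the planning difference in PAHPI points between sides and check the cut-off against it. For a planned improvement of d points, the minimum must be at least 6 + d. If the target remains a 30% fall in score, the minimum is 9, and a higher value would leave room beyond a fall to the floor. If a comparison of proportions is kept, define response and set the minimum so that every entered side can meet it.

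The cost is one eligibility line and a sentence or two in section 9.0. PAHPI is already scored before treatment, so no assessment is added. The downside is a slightly narrower population, excluding people with only faint, small marks, and possibly slower recruitment.

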## **Exclusion Criteria**

- Pregnant patients or patients planning to become pregnant during the time of the study.
- Patients with a history of use of hydroquinone, kojic acid, tretinoin, adapalene, tazarotene or azaleic acid in the previous 3 months
- 5.0 Enrollment/Randomization

Patients presenting to the dermatology clinic with PIH secondary to acne vulgaris and are interested in a potential treatment will be considered as candidates for participation. If their treating physician in clinic determines they are eligible, they will be referred to the PI or sub-PI for screening and consent. The study design and consent will be explained, their expectations for participation will be discussed, and any questions will be addressed. The patient will then have the choice to participate or decline participation in the study. Block randomization will be utilized to determine which side will be the treatment side.

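### The treated side is block-randomised left or right, but section 9.0 uses neither the within-patient pairing nor the randomised side; a paired analysis without a left/right term would lose some power if the two sides differ systematically.

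*Combined protocol and SAP*

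**What the plan says.** This is a split-face trial. Section 6.0 sets up the pairing: "One side of the patient will be chosen as the treatment side, and the other as an intrinsic control". Section 5.0 says how the side is allocated: "Block randomization will be utilized to determine which side will be the treatment side". No block size is given.

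The outcome in section 9.0 is the PAHPI: "Total postacne hyperpigmentation index = S + I + N; score range: 6-22". Baseline is measured: "Patients will be evaluated prior to treatment, and at each follow-up visit", with follow-up at weeks 4, 8 and 12. Change from baseline is therefore available, though it is not named as the analysis.

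On analysis, section 9.0 says only that improvement will be shown "by comparing the treatment side to the control side of the face". The one test named is in the sample-size paragraph: "a sample size of 25 patients is sufficient to detect a clinically important difference of 30" per cent, using a "two-tailed z-test of proportions between two groups of 80% power and a p-value of 0.05". Section 9.0 gives no model, no standard error and no left/right term.

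**The concern.** Blocking keeps the numbers treated on the left and on the right nearly equal. If one side of the face tends to do better than the other whatever is applied to it, that tendency adds to the treated-minus-vehicle difference in about half the patients and subtracts from it in the rest. It nearly drops out of the mean but stays in the spread between patients, and the usual standard error is computed from that spread. The analysis then treats as noise something the randomisation has already controlled.

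The result would be an interval that is too wide, a test run below its nominal 5%, and lost power in a trial of 25 patients planned for 80%.

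**Working it through.** **The plan's own figure.** The 25 cannot be checked, because no control-side proportion is given. For two independent groups with a 30-point difference, n per side = [1.960·√(2p̄(1−p̄)) + 0.842·√(p₁(1−p₁) + p₂(1−p₂))]² / 0.30².

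- 3% vs 33%: [1.960 × 0.5433 + 0.842 × 0.5002]² / 0.09 = 24.5, so 25.
- 20% vs 50%: [1.960 × 0.6745 + 0.842 × 0.6403]² / 0.09 = 38.5, so 39.
- Over other control proportions the result runs from 22 (0 vs 30%) to 43 (35% vs 65%).

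This formula uses neither the pairing nor the side, so the effect of a left/right term has to be examined in a paired model.

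**Inputs.** From the protocol: n = 25, two-sided 5%, 80% power, side allocated in blocks. Assumed, because the documents give no figure: the systematic left-right difference δ, expressed in SDs of the within-patient difference, and near-balanced blocks (a 13/12 split).

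**Model.** D = τ + δ·s + e, where D is the treated-minus-vehicle difference, s = +1 if the left side is treated and −1 if the right, and SD(e) = 1.

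- Without s in the model and with sides balanced, the estimated variance of D is about 1 + δ², while the mean of D varies between repetitions as if the variance were 1. The standard error is too large by √(1 + δ²).
- The approximate type I error is 2·P(t₂₄ > 2.064·√(1 + δ²)). The critical value 2.064 is in effect raised to 2.074, 2.128 and 2.307 for δ = 0.1, 0.25 and 0.5.
- Power comes from simulating the paired t-test at τ = 0.584 SD, the effect that gives 80% power when n = 25 and δ = 0. The extra patient is equally likely to be treated on either side.

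| δ (assumed) | SE ratio | Type I error, no term | Power, no term | With term |
|---|---|---|---|---|
| 0 | 1.000 | 5.0% | 80.2% | 5%; 80.0% |
| 0.10 | 1.005 | 4.9% | 80% | 5%; 80% |
| 0.25 | 1.031 | 4.4% (simulations 4.1-4.4%) | 78% | 5%; 80% |
| 0.50 | 1.118 | 3.0% | 72% | 5%; 80% |

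**The odd patient.** With 25 patients the split cannot be even, and the extra patient shifts the estimate by δ/25. At δ = 0.5, power without the term is about 76% if that patient is always on the side that favours treatment and about 69% if always on the other. The average of the two is the 72% in the table.

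**Is blocking the cause?** Under simple randomisation without the term, simulated type I error stays at 4.8-5.2% for δ up to 1. The conservatism comes from balancing the side and then leaving it out of the analysis.

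**The test actually named.** The unpaired z-test was simulated with a true proportion of 30% on both arms, 25 patients, blocks of 4, and left-right gaps of 0, 10, 20 and 30 points. Type I error by latent within-patient correlation (assumed):

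- correlation 0: 5.5%, 5.3%, 4.7%, 4.1%
- correlation 0.5: 2.1%, 2.0%, 2.0%, 1.9%
- correlation 0.7: 1.0%, 0.9%, 1.1%, 1.2%

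Power at 20% vs 50% hardly moves with the gap: 63.6% to 64.4% at correlation 0, and 66.3% to 66.6% at correlation 0.5.

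**The case against.** The strongest reply is that section 9.0 contains no paired mean analysis to criticise. Omission of the side term is read from silence, and for the only test named the left-right gap matters little once the two sides of a face are correlated. At correlation 0.5 the z-test already runs at about 2% with no gap at all, because it treats paired sides as independent groups. At 0.7 the widest gap makes it slightly less conservative. This stands. A reader might infer that the missing side term is what makes the planned test conservative; the documents do not support that, and ignoring the pairing is the larger fault.

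A reader might also infer that any asymmetry between the sides does this harm. It does not. Asymmetry whose direction varies between patients, for example with sleeping side, is residual error that no side term removes. Stable baseline asymmetry cancels if change from baseline is analysed. Section 4.0 requires bilateral involvement, and section 6.0 has every patient use a standard cleanser and sunscreen over the whole face, which should limit systematic differences arising during treatment.

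Finally, δ is unsupported by any figure in the documents, and at 0.1 SD the effect is negligible. This too stands. What survives is that section 9.0 is the whole analysis text, that it has no place for the factor the randomisation balances, and that the term costs almost nothing once a paired analysis is written.

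**Conclusion.** The point holds as an inexpensive improvement. Section 9.0 uses neither the pairing nor the allocated side. In a paired analysis without the side term, a systematic left-right difference of 0.25 to 0.5 SD would cost about 2 to 8 points of power and widen the interval by about 3% to 12%; at 0.1 SD or less the loss is negligible. These sizes rest on assumed values of δ, near-balanced blocks and a paired t-test on 25 patients, and the true δ in this trial is unknown. The error is in the conservative direction, so the documents give no ground for inferring bias or an excess of false positives.

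**What to change.** In section 9.0, replace the general comparison with a paired analysis. For each patient, take the treated-minus-vehicle difference in PAHPI change from baseline, with each side scored separately. Model that difference with side treated (left = +1, right = -1) as a covariate, and take the intercept as the treatment effect. With this coding the intercept averages left-treated and right-treated patients equally, whichever way the 13/12 split falls. Using change from baseline also removes any stable baseline asymmetry.

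The cost is a sentence or two of text and one degree of freedom, about 0.2 points of power if the sides do not differ. No new data item is needed beyond the allocated side and the per-side scores that the planned comparison already requires. Fixing the term in advance also avoids deciding on it after the data are seen.

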#### 6.0 Study Procedures

Patients with bilateral disease will be chosen to participate in the study. Patients will be advised to discontinue any other facial cleansers or products prior to beginning treatment. One side of the patient will be chosen as the treatment side, and the other as an intrinsic control. Each day, the participant will wash their face in the morning with a standard cleanser, dry their face, then apply the medication to the treatment side of their face only to areas of unwanted dark spots. The patient will then apply the vehicle to the other side of their face only to the areas of unwanted dark spots. The patient will wait 30 minutes, and then apply a standardized sunscreen SPF 30+ to entire face. Each night, the patient will again wash their face. Patients will participate in a follow-up clinic visit 4 weeks, 8 weeks and 12 weeks after beginning treatment. At each visit, photographs will be taken of their face to monitor progression and to serve as a comparison to the control side. The postacne hyperpigmentation index, a validated system for evaluating hyperpigmentation due to acne vulgaris, will be used to monitor the progression of facial lesions. At week 0 and 12, the patients will take a survey to determine the impact that their facial spots have on their quality of life.

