#### 7.0 Risks

Risks of topical TA include skin erythema and irritation. There may also be risks involved with this with this study that are unknown to the researcher at this time.

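### Neither masking of participant and PAHPI scorer nor concealment of the treated side is described, so the only between-side comparison is open to expectation bias

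*Combined protocol and SAP*

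**What the plan says.** Section 5.0 covers allocation in one sentence: "Block randomization will be utilized to determine which side will be the treatment side". It does not say who holds the sequence or whether it is concealed.

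Section 6.0 has the participant wash and dry the face, "then apply the medication to the treatment side of their face only to areas of unwanted dark spots". The next instruction is "The patient will then apply the vehicle to the other side of their face only to the areas of unwanted dark spots". Each visit includes photographs: "photographs will be taken of their face to monitor progression and to serve as a comparison to the control side". PAHPI is used to follow the lesions, but the scorer is not named.

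Section 9.0 sets the efficacy question as improvement shown "by comparing the treatment side to the control side of the face". PAHPI is the sum of size (2 to 8), intensity (3, 6 or 9) and number (1 to 5), with a range of 6 to 22. The intensity item is a visual grade; its middle category, for example, is "Moderately darker than surrounding skin".

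The supplied text, from the background to the references, does not mention blinding, masking, coded or matched containers, an independent assessor, or concealment of the side.

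**The concern.** A vehicle on the control side accounts for the effect of the base. It accounts for expectation only if the participant and the scorer do not know which side is which, and the plan does not say that they do not.

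Knowledge of the side can act in two ways. A scorer who knows it grades both halves of the same face at the same visit and can resolve borderline intensity calls in favour of the treated half. A participant who knows it may care for the two halves differently. Either would appear as a side difference and could not be separated from a drug effect afterwards.

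The plan has no second controlled comparison to fall back on. The quality-of-life survey at weeks 0 and 12 concerns the facial spots in general and is not described as side-specific. The photographs serve the same side comparison, and nothing says they are read with the side hidden.

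**Working it through.** The omission has no figure of its own, so the first part is a reading of the text. The second part is an illustration on assumed inputs.

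**Reading**

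1. *Allocation (Section 5.0).* The side is block-randomised. Concealment is not stated.
2. *Application (Section 6.0).* The instructions use the terms treatment side, medication and vehicle, and fix the order as medication first, vehicle second. This does not show what is printed on the containers. However, a participant who follows the order literally learns the side even from unmarked tubes.
3. *Outcome (Sections 6.0 and 9.0).* The component spans are 8 − 2 = 6 for size, 9 − 3 = 6 for intensity and 5 − 1 = 4 for number, together 16 = 22 − 6. One intensity grade moves the total by 3 of those 16 points.
4. *Scorer and photographs.* Neither the scorer nor the scorer's knowledge of the side is given for PAHPI, and masked reading of the photographs is not stated.

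**Illustration**

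From the plan: 25 patients, a two-sided 5% test and a 3-point intensity step.

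Assumed: no true effect; a paired t-test (Section 9.0 names only a z-test of proportions, for the sample size); an SD of the side difference of 2 to 4 points; and a fraction f of patients shifted one intensity grade toward the treated side.

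- Mean bias: b = 3f, which is 0.15, 0.30 and 0.60 points for f = 5%, 10% and 20%.
- SD including the variance added by the shift: s = √(SD² + 9f(1 − f)).
- Noncentrality: √25 × b / s = 5b/s, with 24 degrees of freedom.

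Worked case, f = 10% and SD = 3: s = √(9 + 0.81) = 3.13; noncentrality = 5 × 0.30 / 3.13 = 0.48; rejection rate 7.5%.

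| Patients shifted | Mean bias (points) | SD 4 | SD 3 | SD 2 |
|---|---|---|---|---|
| 5% | 0.15 | 5.4% | 5.6% | 6.4% |
| 10% | 0.30 | 6.4% | 7.5% | 10.1% |
| 20% | 0.60 | 10.6% | 14.5% | 23.5% |

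Simulating the shifted mixture directly (200,000 runs per cell) gives similar ranges: 5.4–6.1%, 6.3–9.4% and 10.6–22.5%.

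The rate reaches 10% when 9.9% (SD 2), 14.4% (SD 3) or 18.9% (SD 4) of patients are shifted, that is about 2.5, 3.6 or 4.7 of 25.

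With 50 patients under the same model, the ranges rise to 5.8–7.8%, 8.0–15.8% and 16.9–43.0%. A larger sample does not remove a bias of this kind; it makes a false positive more likely.

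**The case against.** The strongest reply is that this is silence, not a stated open design. The front matter was not available and may carry a design label such as double-blind. Medication and vehicle are ordinary protocol terms that a masked trial could also use, and a self-applied vehicle is compatible with an intention to mask. This is right as far as it goes. The finding is that masking is not described, and the evidence is its absence from Sections 5.0, 6.0 and 9.0, not one sentence. A label elsewhere would still leave the scorer unnamed and the application order in Section 6.0 tied to allocation.

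A second reply is that PAHPI is less subjective than the intensity item suggests. Size and number have numeric anchors and supply 6 + 4 = 10 of the 16 points, and Section 6.0 calls the index validated. That also stands, and it limits how much of the score is pure judgement. It does not protect the intensity grade, and it does nothing about unequal care of the two sides.

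A third reply is that the illustration rests on an assumed SD, an assumed one-directional shift and a test the plan does not name. This is true. With an SD of 5 or 6 points, for example, the 20% case gives only 8.7% or 7.6%. The conclusion does not depend on these figures.

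Finally, masking may be imperfect. Section 7.0 states: "Risks of topical TA include skin erythema and irritation". A reaction or a difference in feel could reveal the side. This is why the remedy is claimed to reduce the bias, not to abolish it.

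**Conclusion.** The concern holds for the text available. The plan should be changed on this point, with medium confidence because removed text could already provide masking. Run as written, the trial leaves its only controlled contrast, which rests partly on a visual grade in 3-point steps, exposed to expectation that no later analysis could remove.

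The size of any bias cannot be estimated from the documents. Under the stated assumptions it is negligible if 5% of patients are shifted one grade and material at 20%, with the false-positive rate doubling somewhere between about 10% and 19% of patients. Those figures show sensitivity; they are not a forecast.

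**What to change.** - State in Sections 6.0 and 9.0 whether the participant and the PAHPI scorer are masked, and who scores. If masking is already planned, writing it there and aligning the wording of Section 6.0 is enough.
- Otherwise, dispense active and vehicle in identical containers coded left and right from the randomisation list, with the products matched in appearance as far as possible.
- Reword Section 6.0 in left/right terms, with an order of application that does not depend on allocation.
- Have PAHPI scored by an existing investigator with no access to the list, or score the planned photographs with allocation hidden. Because Section 11.0 has all data deleted at the end of the study, any photograph reading must be finished before then.
- Keep the list out of the data spreadsheet described in Section 10.0, and open it only after the scores are locked.

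**Cost.** Labelling, product matching and a wording change, with no new visit or procedure. The documents do not say who prepares the products or how closely they can be matched. One team member must hold the list and not score. Section 5.0 says of candidates that "they will be referred to the PI or sub-PI for screening and consent", and Section 8.0 mentions co-investigators, so more than one investigator is foreseen; that one can be kept from the list is an assumption. Photograph scoring adds reading time and assumes image quality good enough for PAHPI. Coding the containers also means the sponsor must settle how the side is revealed if a skin reaction calls for it; no rule is proposed here.
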